- Perceived misleadingness of fruit drink
- Perceived product healthfulness of fruit drink for child's daily consumption
- Interest in giving the fruit drink to one's child
- Percent of participants who select an apple-flavored fruit drink rather than bottled water
- Perceived appeal of fruit drink
- Interest in consuming the fruit drink
- Relative harm of the fruit drink compared to soda
- Relative harm of the fruit drink compared to 100% fruit juice

Task 2:

- Perceived product healthfulness of snack
- Product appeal of snack for one's child
- Participant intentions to give snack to one's child
- Intentions to purchase the snack
- Intentions to consume the snack
- Percent of participants able to identify the healthier snack
- Percent of participants able to identify the snack with higher amount of added sugar
- Percent of participants who intend to purchase the snack with higher added sugar
- Perceived message effectiveness of snack
- Social reactions to snack
- Percent of participants who learned something new about the snack
- Snack grabbed the participant's attention
- Label on snack makes participant feel scared
- Thinking about the health effects of the snack

INVESTIGATIONAL PLAN (brief overview)

Study Design

The study design is a between-subjects randomized controlled trial. Qualtrics will randomize participants to one of 12 study arms where they will see one of four versions of fruit drinks and one of three versions of granola snacks upon entering into a virtual convenience store (iShoppe).

Fruit drink versions (task 1):

1. control (no nutrition-related claim)
2. “100% Vitamin C daily value” claim
3. “100% All Natural” claim
4. “No artificial sweeteners” claim

Granola snack versions (task 2):

1. control (neutral barcode label)
2. "WARNING: High in added sugar" text warning label
3. warning label with an image of sugar cubes in a cup along with the text "WARNING: High in added sugar"

12 Study Arms

Arm	Label	Cooler A	Cooler B	Snack 1	Snack 2
1	Control (no claim)	Grape fruit drink v. grape juice	Apple fruit drink v. water	No label	Text
2	Control (no claim)	Grape fruit drink v. grape juice	Apple fruit drink v. water	No label	Barcode
3	Control (no claim)	Grape fruit drink v. grape juice	Apple fruit drink v. water	No label	Graphic
4	Claim 1 – No Artificial Sweeteners	Grape fruit drink v. grape juice	Apple fruit drink v. water	No label	Text

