5. Self-identify as non-Hispanic white, non-Hispanic Black, or Hispanic any race
6. Panel member on CloudResearch and/or Kantar

STUDY PROCEDURES (what will be done)

Study Steps

Panel Companies will reach out to panel members about this research study. If interested, panel members will complete a screener in Qualtrics to see if they are eligible. If they are not eligible, panel members will be redirected to a termination page indicating they are not eligible to participate. If they are eligible, panel members will be redirected to a consent form. If they agree to the consent form, they will acknowledge their consent by clicking an arrow to proceed to the study.

Qualtrics will randomize the participant to one of the twelve study arms and redirect the participant to iShoppe. In iShoppe the participant will be instructed to shop for their child who is between 1-5 years old. If they have more than one child aged 1-5, they will be instructed to think about the child who had their birthday most recently. They will then be instructed to select two beverages for their child. They will compare the two beverage options for each selection task (grape fruit drink vs. 100% grape fruit juice; apple fruit drink vs. water) and choose one of each. Once they have selected the two beverages, they will be instructed to select a granola snack (control snack with no label vs. experimental snack with label). Once all three products are in the participants' shopping basket, iShoppe will then redirect them to another Qualtrics survey. In the Qualtrics survey, participants will answer questions about their perceptions about and reactions to the fruit drinks and snack, as well as standard demographic questions (see measurements section for more detail). Upon completing the survey, participants will be redirected to a termination link where they will receive an incentive in a type and amount set by the panel company.

Subject Completion/ Withdrawal procedures

A study participant is determined to have completed the study when they have finished and exited the study survey. To withdraw their data from the study, a participant would have to contact the study team or the university IRB.

Screen failure procedures

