Compared to regular (non-diet) soda , this beverage is...	1=Much less healthy 2=Slightly less healthy 3=Similarly healthy 4=Slightly healthier 5=Much healthier
Compared to 100% fruit juice , this beverage is...	1=Much less healthy 2=Slightly less healthy 3=Equally healthy 4=Slightly healthier 5= Much healthier
Do you think this beverage has added sugar?	0=No [coded as misperception] 1=Yes
[skip if previous Q=0. Will enter 0 as response their response] A can of regular soda contains 8 teaspoons of added sugar. How many teaspoons of added sugar do you think this beverage has?	[free-text entry of #, restrict responses between 0 and 100] _____ teaspoons
This beverage is 20% fruit juice and contains 39 grams (about 9 teaspoons) of added sugar.	1=Not at all misleading 2=A little misleading

How misleading do you think the information on this product is?	3=Somewhat misleading 4=Very misleading 5=Extremely misleading
Secondary measures: Task 2	
[Display labeled snack per their assigned condition] How healthy would it be for your [age] year old child to eat this snack every day?	1=Very unhealthy 2=Slightly unhealthy 3=Neither healthy nor unhealthy 4=Slightly healthy 5=Very healthy
How appealing would your [age] year old child find this snack?	1=Very unappealing 2= Somewhat unappealing 3=Neither appealing nor unappealing 4=Slightly appealing 5=Very appealing
How likely would you be to give this snack to your [age] year old child?	1=Not at all likely 2=A little likely 3=Fairly likely 4=Very likely 5=Extremely likely
How likely would you be to buy this snack in the next week, if it were available?	1=Not at all likely 2=A little likely 3=Fairly likely 4=Very likely 5=Extremely likely
How likely would you be to eat this snack?	1=Not at all likely 2=A little likely 3=Fairly likely 4=Very likely 5=Extremely likely
Which of these snacks do you think would be healthier for your [age] year old child?	1 = (image of product with warning label) 2 = (image of product without warning label) (Randomize their order)
Which of these snacks do you think is higher in added sugar?	1 = (image of product with warning label) 2 = (image of product without warning label) (Randomize their order)
Which of these snacks would you most want to buy for your [age] year old child?	1 = (image of product with warning label) 2 = (image of product without warning label) (Randomize their order)

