### **Analyses**

We will report descriptive results for all outcomes (i.e., means and proportions by group). In all models, the predictor will be a dummy variable indicating whether the participant was randomized to one of the three intervention nutrition claim conditions. For predictions with Likert-style outcomes, we will run linear regression models, one for each outcome. We will examine skewness of the residuals and run ordinal models in sensitivity analyses if residuals

are skewed, retaining the linear models if the pattern of results does not change. For predictions with dichotomous outcomes, we will use the same approach except with logistic regression. We will use the margins command in Stata for significance testing of control vs. each claim separately, as well as each claim compared to the other claims.

We will also report results when controlling for any participant demographic characteristics (including random assignment to two experiments conducted after the primary outcome, but before measurement of some of the secondary outcomes) found to be unbalanced across treatment arms in balance tests, if these results differ substantively from unadjusted results (i.e., changes in statistical significance or direction of effect).

We will examine whether the following participant characteristics moderate the effect claims on the primary outcome:

- a) Age of child shopping for (in years);
- b) Gender of parent (man vs. woman);
- c) Gender of child (boy vs. girl);
- d) Race/ethnicity of parent (White non-Hispanic vs. Black non-Hispanic vs. Hispanic);
- e) Low educational attainment (dichotomized based on sample distribution);
- f) Household income (dichotomized based on sample distribution);
- g) Child's frequency of consuming fruit drinks (above vs. at or below the sample median);
- h) Time spent looking at Nutrition Facts Panel of the beverage;
- i) Seeking vitamin C since COVID-19 pandemic

To test whether these characteristics moderate the effect of claims on selection, we will fit a series of logistic regressions models (one for each potential moderator), with trial arm, the moderator, and their interaction as predictors. We will probe significant interactions by calculating the marginal effect of nutrition claims on the outcome at different levels of the moderating variable.

We will use a critical alpha of 0.05 and statistical tests will be two-tailed. We will correct for multiple comparisons.

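### Task 1 survey outcomes follow a randomised sugar warning, but the plan models that assignment only if a balance test flags it, and never looks at claim effects by label

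*SAP*

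**What the plan says.** The design crosses two factors. Protocol, Study Design: "Qualtrics will randomize participants to one of 12 study arms where they will see one of four versions of fruit drinks", together with one of three snack-label versions (neutral barcode, text warning, warning with picture). Both warning versions carry the same statement that the snack is high in added sugar. In the 12 Study Arms table, the barcode is in arms 2, 5, 8 and 11, and a warning is in the other eight.

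The order is fixed. Protocol, Study Steps: "Once they have selected the two beverages, they will be instructed to select a granola snack". The survey comes after all three choices. The protocol lists 12 Task 1 secondary outcomes. One of them, apple drink versus water, is a shopping choice made before the snack. The other 11 are survey items, among them "Do you think this beverage has added sugar" and the number of teaspoons.

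In SAP, Task 1, Analyses, claim condition is the only default predictor. The plan acknowledges random assignment to two experiments that fall after the primary outcome but "before measurement of some of the secondary outcomes". It controls for that assignment only if balance tests find it uneven, and reports the controlled result only if significance or direction changes. Protocol, Statistical Methods, Task 1 has the same rule. The nine listed moderators apply to the primary outcome only, and snack label is not among them. The Task 2 analysis uses a matching conditional rule for experiments that came earlier.

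**The concern.** The snack warning and several of the survey items concern the same thing, added sugar. A parent who has just met a sugar warning may answer differently about a fruit drink, and the drink's claim may mislead that parent less, or more, than it would otherwise have done.

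A balance test does not address this. Label is randomised across claim arms, so an uneven split is chance and an even split says nothing about whether the claim effect depends on label. Nor does the plan contain any other analysis that could show such a dependence. The second condition, reporting the adjusted result only when it changes the conclusion, also makes what is reported depend on the results.

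At stake is the interpretation of the misperception outcomes. The protocol's background says that evidence of misperceptions could inform legal action and regulation of claims. The tasks are to be published as separate papers, so a Task 1 reader may not learn that most arms had also been shown a sugar warning.

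**Working it through.** **The plan's own figure.** The only power statement (Protocol, Sample Size and Power) is 80% at about 2,170 participants for f = 0.06 on the Task 1 primary outcome. A two-group comparison (any claim versus none, 1 df) gives 79.8%, so the figure reproduces on that reading; with four groups (3 df) power is 64.2%. No figure is given for the survey outcomes, so this neither supports nor weakens the point.

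**Exposure.** Warning arms are 8/12 = 66.7%. Equal allocation is not stated and is assumed from here on. With N = 2,175, n = 2,175/12 = 181.25 per cell.

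**What the planned contrast estimates.** Averaged effect = (barcode effect + 2 × warning effect)/3. All effects below are assumed.
- 10 points after barcode, 2 after a warning: (10 + 4)/3 = 4.7 points.
- 10 and 4: (10 + 8)/3 = 6.0 points.
- 4 and 10: (4 + 20)/3 = 8.0 points.
- Equal effects: the average equals the barcode effect, and nothing is lost.

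Whether effects differ depends on the scale. Suppose claims have an odds ratio of 1.5 under every label, and a warning lowers the control belief rate from 40% to 20%. After the barcode the odds go from 0.667 to 1.0, so 40% becomes 50%, an effect of 10.0 points. After a warning the odds go from 0.25 to 0.375, so 20% becomes 27.3%, an effect of 7.3 points. The average is (10.0 + 2 × 7.3)/3 = 8.2 points, with no interaction on the log-odds scale.

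**Does adjustment change this?** In 400 simulated trials of 2,170, with an assumed claim effect of 0.30 SD under barcode and 0 under warning, the expected average is 0.30/3 = 0.10. The unadjusted model gave 0.098, the model with label as a main effect gave 0.098, and the model with the interaction gave 0.307 for the barcode arms. Only the last separates the two.

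**How often would the balance rule act?** In 2,000 simulated randomisations, a 5% chi-squared test on the 4 × 3 table of claim by label flagged imbalance 5.3% of the time, which is the false-positive rate and no more.

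**Precision, any claim versus control, assumed belief rate 40%** (variance 0.4 × 0.6 = 0.24).
- All arms: √(0.24/543.75 + 0.24/1,631.25) = 2.4 points.
- Barcode arms only: √(0.24/181.25 + 0.24/543.75) = 4.2 points, which is √3 = 1.7 times larger.
- Claim-by-warning interaction: √(0.24 × (1/n + 1/3n + 1/2n + 1/6n)) = √(0.24 × 2/181.25) = 5.1 points.
- Interaction detectable with 80% power: 2.80 × 5.146 (the SE before rounding) = 14.4 points.
- Power for the 6 to 8 point differences in the first two illustrations: about 21% to 34%.

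For outcomes on a standardised scale (N = 2,170), the detectable effects are 0.139 SD averaged over labels, 0.241 SD within the barcode arms and 0.295 SD for the interaction.

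**The case against.** The strongest reply is that nothing is biased. Label is randomised and crossed with claim, the SAP's predictions are directional statements about claim versus no claim, and the averaged contrast tests those validly. This stands. A reader might infer that the warning confounds the Task 1 survey results; the design rules that out.

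There are also reasons to expect a modest interaction or none. The warning is on a different product. The drink is shown again, in its assigned condition, when the questions are asked. If the survey follows the order of the measures table, prior exposure is a single snack choice. A general sugar cue could move beliefs equally in all claim arms and leave a difference in means or percentage points unchanged. These facts make a large effect less certain but do not exclude one, and the plan has no analysis that would tell.

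It is fair, too, that the documents never name claims under current labelling as the target of Task 1. A reader might infer that target from the background on regulation, but it is not stated, so the average cannot be called the wrong quantity. What can be said is that the plan does not describe it as an average.

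Finally, reporting by label over 11 outcomes adds many weak comparisons. That is a good reason to label them exploratory, but not to leave them out.

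**Conclusion.** The point holds as one of analysis rule and interpretation, and it is confined to the 11 survey outcomes of Task 1. The balance test is the wrong condition for including a randomised crossed factor, and the plan cannot show whether claim effects differ after a warning. The primary outcome and the apple-versus-water choice precede the snack and are untouched.

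The size is unknown. In the assumed scenarios the averaged effect is 40% to 53% below the no-warning effect (6.0 or 4.7 against 10) or double it (8.0 against 4). These figures rest on assumed effects and equal allocation, and the departure is zero if claim and label do not interact on the scale reported.

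Two stronger readings are not supported. Including label as a main effect would not remove the averaging. And the SAP and protocol do not contradict each other over the two experiments: both use that number, and neither says what the two are. Snack label is the only later experiment described as an arm. Displayed flavour is also randomised in the survey, but the documents do not say whether it is the second.

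**What to change.** 1. In every Task 1 survey model, include snack-label arm (barcode, text, graphic) and displayed flavour as factors regardless of balance, and include claim arm in every Task 2 model. Drop the balance-test condition and the rule on when to report for these randomised factors. This can improve precision; it does not change what is averaged.
2. State that Task 1 survey effects are averaged over snack-label exposure. Add a table of claim effects by label (barcode versus warning) with the interaction, labelled exploratory and kept outside the multiplicity-corrected tests. Identify the barcode-arm estimate as the one without prior warning exposure.
3. Name the two experiments in both documents, so that both assignments are in the models.

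The cost is a few model terms, some further margins calls and one table; no new data are needed. The limits should be written next to the table. Barcode-arm standard errors are about 1.7 times larger, so those estimates support the averaged ones and do not replace them. The interaction test would usually miss a difference smaller than about 14 points (40% belief rate and equal allocation assumed), so a non-significant result does not show that the claim effect is the same with and without a warning.

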We will report descriptive results for all outcomes (i.e., means and proportions by group). In all models, the predictor will be a dummy variable indicating whether the participant was randomized to one of the three intervention nutrition claim conditions. For predictions with Likert-style outcomes, we will run linear regression models, one for each outcome. We will examine skewness of the residuals and run ordinal models in sensitivity analyses if residuals are skewed, retaining the linear models if the pattern of results does not change. For predictions with dichotomous outcomes, we will use the same approach except with logistic regression. We will use the margins command in Stata for significance testing of control vs. each claim separately, as well as each claim compared to the other claims.

We will also report results when controlling for any participant demographic characteristics (including random assignment to two experiments conducted after the primary outcome, but before measurement of some of the secondary outcomes) found to be unbalanced across treatment arms in balance tests, if these results differ substantively from unadjusted results (i.e., changes in statistical significance or direction of effect).

We will examine whether the following participant characteristics moderate the effect claims on the primary outcome:

- a) Age of child shopping for (in years);
- b) Gender of parent (man vs. woman);
- c) Gender of child (boy vs. girl);
- d) Race/ethnicity of parent (White non-Hispanic vs. Black non-Hispanic vs. Hispanic);
- e) Low educational attainment (dichotomized based on sample distribution);
- f) Household income (dichotomized based on sample distribution);
- g) Child's frequency of consuming fruit drinks (above vs. at or below the sample median);
- h) Time spent looking at Nutrition Facts Panel of the beverage;
- i) Seeking vitamin C since COVID-19 pandemic

To test whether these characteristics moderate the effect of claims on selection, we will fit a series of logistic regressions models (one for each potential moderator), with trial arm, the moderator, and their interaction as predictors. We will probe significant interactions by calculating the marginal effect of nutrition claims on the outcome at different levels of the moderating variable. We will use a critical alpha of 0.05 and statistical tests will be two-tailed. We will correct for multiple comparisons.

Task 2

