We will report descriptive results for all outcomes (i.e., means and proportions by group). In all models, the predictor will be a dummy variable indicating whether the participant was randomized to one of the two warning message conditions. For predictions with Likert-style outcomes, we will run linear regression models, one for each outcome. We will examine skewness of the residuals and run ordinal models in sensitivity analyses if residuals are skewed, retaining the linear models if the pattern of results does not change. For predictions with dichotomous outcomes, we will use the same approach except with logistic regression. We will use the margins command in Stata for significance testing of control vs. each warning message separately, as well as each warning message compared to each other. We will also report results when controlling for any participant demographic characteristics (including random assignment to experiments conducted before the primary outcomes) found to be

unbalanced across treatment arms in balance tests, if these results differ substantively from unadjusted results (i.e., changes in statistical significance or direction of effect).

We will examine whether the following participant characteristics moderate the effect claims on the primary outcome:

- a) Age of child shopping for (in years);
- b) Gender of parent (man vs. woman);
- c) Gender of child (boy vs. girl);
- d) Race/ethnicity of parent (White non-Hispanic vs. Black non-Hispanic vs. Hispanic);
- e) Low educational attainment (dichotomized based on sample distribution);
- f) Household income (dichotomized based on sample distribution);
- g) Time spent looking at Nutrition Facts Panel of the snack;

To test whether these characteristics moderate the effect of warning messages on selection, we will fit a series of logistic regressions models (one for each potential moderator), with trial arm, the moderator, and their interaction as predictors. We will probe significant interactions by calculating the marginal effect of sugar warnings on the outcome at different levels of the moderating variable. We will use a critical alpha of 0.05 and statistical tests will be two-tailed. We will correct for multiple comparisons.

Sample Size and Power

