### Analyses

We will report descriptive results for all outcomes (i.e., means and proportions by group). In all models, the predictor will be a dummy variable indicating whether the participant was randomized to one of the two warning message conditions. For predictions with Likert-style outcomes, we will run linear regression models, one for each outcome. We will examine skewness of the residuals and run ordinal models in sensitivity analyses if residuals are skewed, retaining the linear models if the pattern of results does not change. For predictions with dichotomous outcomes, we will use the same approach except with logistic regression. We will use the margins command in Stata for significance testing of control vs. each warning message separately, as well as each warning message compared to each other. We will also report results when controlling for any participant demographic characteristics (including random assignment to experiments conducted before the primary outcomes) found to be unbalanced across treatment arms in balance tests, if these results differ substantively from unadjusted results (i.e., changes in statistical significance or direction of effect).

We will examine whether the following participant characteristics moderate the effect claims on the primary outcome:

- a) Age of child shopping for (in years);
- b) Gender of parent (man vs. woman);
- c) Gender of child (boy vs. girl);
- d) Race/ethnicity of parent (White non-Hispanic vs. Black non-Hispanic vs. Hispanic);
- e) Low educational attainment (dichotomized based on sample distribution);
- f) Household income (dichotomized based on sample distribution);
- g) Time spent looking at Nutrition Facts Panel of the snack;

To test whether these characteristics moderate the effect of warning messages on selection, we will fit a series of logistic regressions models (one for each potential moderator), with trial arm, the moderator, and their interaction as predictors. We will probe significant interactions by calculating the marginal effect of sugar warnings on the outcome at different levels of the moderating variable.

We will use a critical alpha of 0.05 and statistical tests will be two-tailed. We will correct for multiple comparisons.

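### Adjustment covariates are chosen by balance tests and shown only if the conclusion changes; a short pre-specified adjustment, always reported, would be more transparent and slightly more precise

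*SAP*

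**What the plan says.** The SAP (Task 1 and Task 2, Analyses) defines the treatment-effect models by the randomised condition alone: "In all models, the predictor will be a dummy variable indicating whether the participant was randomized" to an intervention condition. No covariate list is given.

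Adjustment is a supplementary step with two conditions. A characteristic must be "found to be unbalanced across treatment arms in balance tests, if these results differ substantively from unadjusted results"; the plan defines a substantive difference as a change in significance or in the sign of the effect. No threshold for the balance test is stated.

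Assignment to other experiments is put through the same test. Task 1 includes assignment to "two experiments conducted after the primary outcome, but before measurement of some of the secondary outcomes"; Task 2 has the parallel phrase "including random assignment to experiments conducted before the primary outcomes".

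The protocol (Statistical Methods, Task 1 and Task 2) repeats the rule, beginning "We will also report results when controlling for any participant demographic characteristics". Participant characteristics otherwise appear only in the moderator models, with an interaction term. For both tasks the SAP adds "We will correct for multiple comparisons", without naming a method.

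**The concern.** Three features of the rule are weak.

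- **Selection.** Among everyone randomised, an imbalance between arms is chance. The test therefore picks variables for their imbalance, not for how well they predict product choice. A strong predictor that happens to be balanced is never used, and the main estimate gains no precision from data already collected.
- **Display.** Whether the adjusted estimate appears depends on what it shows. When it agrees with the unadjusted one, readers see neither it nor its interval. When it does appear, it will mostly be because a p-value crossed 0.05.
- **Other randomised assignments.** Claim version and snack label are design factors. Where one precedes an outcome of the other task, it can simply be a model term; a balance test adds nothing to that decision.

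At stake are modest precision and a reporting rule that does not depend on the result.

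**Working it through.** **Inputs.** From the protocol (Sample Size and Power): N about 2,170, f = 0.06, alpha 0.05, power 80%. From the SAP: target about 2,175, two-tailed tests. From the protocol (Study Design): four claim versions crossed with three snack versions in 12 arms. Assumed: equal allocation, a balance-test threshold of 0.05, and R² of 0.01, 0.05 or 0.10.

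**1. The plan's own figure.** With two equal groups, noncentrality N·f² = 2,170 × 0.0036 = 7.81 gives power 79.8%; N = 2,183 gives 80%. The stated figure is reproduced as a two-group comparison, for which d = 2f = 0.12.

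**2. Power with adjustment.** Adjustment reduces the residual variance by the factor 1 − R², so the effective d is 0.12/√(1 − R²): 0.1206, 0.1231 and 0.1265. Noncentral t, two-sided 0.05:

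| Contrast | R² 0 | 0.01 | 0.05 | 0.10 |
|---|---|---|---|---|
| One claim vs control, 543 per arm (2,170/4) | 50.6% | 51.0% | 52.7% | 54.9% |
| Any claim vs control, 1,628 vs 542 | 67.7% | 68.1% | 69.9% | 72.2% |
| One warning vs control, 725 per arm (2,175/3; d carried over as an assumption) | 62.7% | 63.1% | 64.9% | 67.3% |

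If f = 0.06 is instead taken to hold for the 1:3 split itself (d = 0.06/√0.1875 = 0.139), the any-claim figures are 79.8%, 80.2%, 81.8% and 83.8%. The gain is again about 0.4 to 4 points.

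**3. Equivalent sample size.** 2,175/(1 − R²) − 2,175 = 22, 114 and 242 participants.

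**4. Interval width.** For an assumed 50% vs 56% with 543 per arm, the 95% half-width is 1.96 × √[(0.25 + 0.2464)/543] = 5.93 points. Multiplying by √(1 − R²) gives 5.90, 5.78 and 5.62.

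**5. What the balance rule recovers.** Four independent tests at 0.05 flag at least one covariate with probability 1 − 0.95⁴ = 18.5% under correct randomisation; seven give 30%. A logistic simulation (4,000 trials per setting, four covariates) compared variance reduction if the balance-selected model were taken as the main result with that from pre-specified adjustment. The pairs were 0.1% vs 1.0%, 1.1% vs 5.3% and 1.7% vs 9.2% at the three R² values. Simulated power under the balance rule barely differed from unadjusted power.

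**6. How often the adjusted result would be seen.** A simulation with seven independent covariates, 1:3 allocation and R² of 0.02 to 0.10 showed it in 2.0% to 4.4% of trials under the null and 1.1% to 2.5% at the design effect. Counting either analysis as a success gave type I error of 5.1% to 5.3%, against 4.9% to 5.0% for the unadjusted test.

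**7. Missing covariates.** Complete-case analysis losing 5% leaves 516 per arm. At R² 0.05, power is then 50.6%, the same as with no adjustment.

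**8. Which variables qualify.** Standard demographics are asked after shopping (protocol, Study Design), so only characteristics that exposure cannot change are safe. "Time spent looking at Nutrition Facts Panel of the beverage" is not: it accrues while the labelled product is on view, and the protocol's Background itself says claims make people less likely to seek further nutrition information.

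**9. Other assignments.** The snack is chosen after the beverages (protocol, Study Steps), so claim version precedes the Task 2 choice and snack label precedes all survey items. The protocol's measurement table also randomises which drink, apple or grape, is displayed for the Task 1 items. The SAP counts two experiments after the Task 1 primary outcome but names neither; whether the drink display is the second one is not stated.

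**The case against.** The strongest reply is that nothing in the plan is wrong. The arm-only model is pre-specified and always reported, and the display rule is itself stated in advance. It discloses the adjusted result exactly when that result would change the conclusion. Type I error scarcely moves even if either analysis counts as a success. All of this stands. A reader might infer that the comparisons are biased or that the rule lets the investigators substitute a favourable analysis. The documents do not support that, because adjusted results are reported in addition to the unadjusted ones.

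A second reply is that the gain rests on an R² found nowhere in the documents. This also stands. A reader might be tempted by larger gains at R² of 0.20, but nothing in the documents supports that value, and at 0.01 the gain is trivial. The argument for consistent reporting does not need R².

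A third is that balance checks have a use. It would be tempting to conclude that they should be dropped altogether. But the SAP recruits until about 2,175 people have completed the survey, and demographics come late. Imbalance among completers could therefore reflect differential drop-out as well as chance. The checks should stay as a diagnostic and only lose their role in choosing covariates.

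Finally, claim and snack versions are fully crossed, so they are independent by design apart from chance. Entering the other assignment as a fixed term is tidier than testing it, but no precision gain has been shown for it.

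**Conclusion.** The point holds as a cheap improvement in precision and reporting, not as a failure of validity. Selecting covariates by imbalance recovers little of the available precision, and the display rule means readers would rarely see an adjusted estimate. Under assumed R² of 0.01 to 0.10, pre-specified adjustment adds about 0.4 to 4 power points for one claim against control and 0.4 to 4.5 for any claim against control. These figures also assume equal allocation, f = 0.06 read as d = 0.12, and almost no participants lost to missing covariates. Reporting both results regardless of agreement is worthwhile whatever R² proves to be.

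**What to change.** Change both Analyses sections of the SAP and the matching protocol text.

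- Stop using balance tests to select covariates. Keep a baseline table and a check of completion by arm as a diagnostic for differential drop-out.
- For each outcome, pre-specify as the lead model the arm factor plus race/ethnicity quota group, child age, parent education and household income. Add the child's fruit-drink frequency for Task 1 only if it is asked before shopping. Exclude time on the Nutrition Facts Panel.
- Fix the coding of each covariate in advance (education and income cut-points are now left to the sample distribution). Retain participants with missing covariates, for example through a missing category or simple imputation.
- For dichotomous outcomes, estimate marginal risk differences with the planned margins command, since an adjusted odds ratio is conditional and its standard error need not shrink.
- Always report adjusted and unadjusted results side by side, and apply the planned multiplicity correction to the lead model.
- Where another randomised exposure precedes an outcome, enter it as a fixed term without a balance test: claim version for Task 2, snack label for the Task 1 survey items, and the apple-or-grape display for the Task 1 items that show one drink. The Task 1 primary choice needs none of these.
- Name the two experiments that the Task 1 text counts.

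Cost: SAP wording, a few model terms, a coding and missing-covariate rule, and a longer results table. The four core covariates need no new data; fruit-drink frequency needs its place in the questionnaire confirmed.
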